6.1.3.1 Perifosine related toxicity

Dose Modifications for Toxicity During the Loading Dose: Nausea and vomiting are the only toxicities likely to occur during the loading dose that may require dose modification. In patients who have emesis and are unable to retain perifosine, every attempt should be made to obtain control of nausea and vomiting using additional antiemetic medication. The dose of perifosine may be repeated if emesis occurs within 30 minutes of taking the tablet(s) OR all the tablets are seen in the emesis.

Dose Modifications for Toxicity during Maintenance Dosing:
For Grade 1 toxicity, treatment with perifosine will not be interrupted.

For Grade 2 nausea, vomiting, or diarrhea:

- (a) For nausea, vomiting and diarrhea, maintain dosing with symptomatic treatment. The dose of perifosine may be repeated if emesis occurs within 30 minutes of taking the tablet(s) OR all the tablets are seen in the emesis.
- (b) For persistent nausea, vomiting or diarrhea despite symptomatic treatment that remains unacceptable to the patient, hold both agents and then reduce dose of each by one dose level. If patients are receiving 50 mg/day of perifosine maintenance at the time of occurrence/recurrence of toxicity, change the schedule of administration to 50 mg every other day (q 2 days, dose level -2) Reductions below this dose/schedule will not be allowed.

For grade 3 joint pain (gout):

Hold perifosine and start allopurinol and/or other agents at the discretion of the investigator. Reevaluate the patient at least weekly (more frequently is allowed) until toxicity improves to \leq Grade 1 or grade 2 that is acceptable to the patient. Then reduce the maintenance dose of perifosine by one dose level. If patients are receiving 50 mg/day at the time of occurrence/recurrence of toxicity, change the schedule of administration to 50 mg every other day (q 2 days, dose level -2). Reductions below this dose/schedule will not be

Amended:

Reviewed by OCR, JR 3/24/14

Memorial Sloan Kettering Cancer Center
IRB Protocol

IRB#: 09-058 A(14)

allowed.

For Unresolved Toxicity

If a patient has unresolved toxicity (which have not returned to \leq grade 1 or grade 2 that is acceptable to the patient OR to within 1 grade of starting values for pre-existing laboratory abnormalities) greater than 14 days from the last dose of both temsirolimus and perifosine, the patient should discontinue all treatment and be taken off study. However, if it is the treating physician's opinion that the patient may benefit from continued treatment, the patient may continue on study with a dose reduction. Dose reduction below 50 mg PO q 2 days are not allowed unless it is the opinion of the treating physician that the patient may benefit from continued treatment. The decision to proceed with treatment must be made in consultation with the PI and the CTEP Senior Investigator/Medical Monitor.

Amended:

Reviewed by OCR, JR 3/24/14

Table 6: Summary of Dose Modification for perifosine and temsirolimus

Toxicity	Perifosine	Temsirolimus
Hematologic	Continue drug; no dose reduction	Hold drug and reduce dose per Section 6.1.2 and dose levels in table 4
Rash	Continue drug; no dose reduction	Hold temsirolimus and reduce dose per Section 6.1.3 and dose levels in table 4 . Consider Dermatology consultation.
Diarrhea, nausea, vomiting	Hold perifosine first. Resume at same dose after improvement per section 6.1.3 and Table 5 . If no improvement, hold and reduce dose per section 6.1.3 and dose levels in Table 5 . Consider GI consultation	If no improvement after holding perifosine, hold temsirolimus and reduce dose per section 6.1.3 and dose levels in table 4 . Consider GI consultation.
Stomatitis	Continue drug; no dose reduction	Hold temsirolimus and reduce dose per Section 6.1.3 and dose levels in table 4 . Consider GI consultation.
Pulmonary	Continue drug; no dose reduction	Hold drug per Section 6.1.3
Hepatic	Continue drug; no dose reduction	Hold drug and reduce dose per Section 6.1.3 and dose levels in table 4
Hyperlipidemia	Continue drug; no dose reduction	Hold drug and reduce dose per Section 6.1.3 and dose levels in table 4 . Initiate antilipid therapy
Joint pain/gout attack	Hold perifosine. Start allopurinol 300 mg per day or other regimen at discretion of investigator. If persists, hold perifosine. Reduce dose per section 6.1.3.1 and dose levels in Table 5 . Continue allopurinol at same or increased dose with other agents at the discretion of the investigator to treat gout.	Continue drug; no dose reduction

Amended:

Reviewed by OCR, JR 3/24/14

All other toxicities	Continue drug; no dose reduction	Hold drug and reduce dose per Section 6.1.3 and dose levels in table 4 except Subjects with toxicities that are manageable with supportive therapy do not require dose reductions unless they remain grade 3 or unacceptable grade 2 despite maximal medical therapy
----------------------	----------------------------------	--

6.1.4 At the Start of the Next Treatment Cycle:

Additional cycles of therapy may be administered provided that the patient meets the following criteria on Day 1 of each cycle (labs may be drawn up to 3 days before the start of the cycle):

- ANC \geq 1,000/mcL
- Platelets \geq 100,000/mcL
- Non-hematologic toxicity recovered to \leq grade 1 (or tolerable grade 2) EXCEPT
 - Non-hematologic toxicities such as rash, diarrhea and mucositis will only be considered a DLT if they remain grade 3 or unacceptable grade 2, despite maximal medical therapy.
 - *Hypercholesterolemia and hypertriglyceridemia and other Metabolism and Nutrition Disorders (such as hypophosphatemia and hypocalcemia) will only be considered a DLT if it remains grade 3 or unacceptable grade 2, despite maximal medical therapy.
- No evidence of progressive disease

In the event of toxicity, the doses of temsirolimus will be adjusted according to the guidelines shown in the Dose Delays/Dose Modifications [table7](#) below. If an adverse event is not covered in the table, doses may be reduced or held at the discretion of the investigator for the subject's safety. Dose adjustments for hematological toxicity are based on the blood counts obtained in preparation for the day of treatment.

Patients requiring dose reductions should not have the dose re-escalated with subsequent treatments.

Subjects with toxicities that are manageable with supportive therapy do not require dose reductions unless they remain grade 3 or unacceptable grade 2 despite maximal medical therapy: hyperlipidemia may be treated with statins, such as pravastatin (which does not affect cytochrome metabolism), extended release niacin, or gemfibrozil; nausea/vomiting may be treated with antiemetics; and diarrhea may be treated with loperamide rather than by dose reduction

Subjects will be withdrawn from the study if they fail to recover to CTC Grade 0-1 or tolerable grade 2 (or within 1 grade of starting values for pre-existing laboratory abnormalities) from a treatment-related toxicity (EXCEPT toxicities that are manageable with supportive therapy as above) within 14 days from the last dose of both temsirolimus and perifosine OR they experience agent related adverse events requiring dose modification despite two previous dose reductions (i.e. would require a 3rd dose reduction) unless the investigator, PI, and CTEP monitor agree that the subject should remain in the study because of evidence that the patient is/may continue deriving benefit from continuing study treatment. The appropriate reduced dose will be determined after discussion between the principal investigator and CTEP monitor.

Amended:

Reviewed by OCR, JR 3/24/14

Table 7

Adverse Event	Agent	Treatment Modifications
Blood/Bone Marrow		
Grade 3: Neutrophils ANC 500-1000 Platelets 50,000-75,000	Temsirolimus	
 Delay Temsirolimus until recovery to \leq grade 1. Retreat at a one dose level reduction If recovery requires > 14 days from the last dose of both temsirolimus and perifosine, discontinue all study treatment.
Grade 4: Neutrophils ANC < 500 Platelets $< 25,000$		
 Delay Temsirolimus until recovery to \leq grade 1. Retreat at two dose levels reduction If recovery requires > 14 days from the last dose of both temsirolimus and perifosine, discontinue all study treatment.
Pulmonary/Upper Respiratory		
Pneumonitis (cough, dyspnea, fever)	Temsirolimus	Discontinue Temsirolimus pending investigation. If diagnosis is confirmed and events are considered at least possibly due to Temsirolimus, the agent is removed from the study.
All other non-hematologic adverse events except nausea, vomiting, and diarrhea		
Grade 0-2	Temsirolimus	Grade 2 toxicities that are persistent and intolerable (i.e. stomatitis) can result in dose delays and dose reductions to the next lower dose level
Grade 3-4		
Hold dose.
 
 Re-evaluate until AE resolved to \leq 1 or tolerable grade 2. Re-treat at a one dose level reduction If recovery requires > 14 days from the last dose of both temsirolimus and perifosine, discontinue all study treatment. Patients with grade 4 AEs related to agent may be taken off study at investigator's discretion.

6.1.5 For treatment or dose modification related questions, please contact the PI at [contact] or [contact].

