6.1.3 Non-hematologic toxicity

Dose Modifications Based on perifosine and temsirolimus-related Non-Hematologic Toxicities and dose adjustments for each drug shown in [tables 4, 5, and 6](#):

NCI Grade	% of Planned perifosine and temsirolimus dose
0-2+	100%+
3*	hold**
4	hold***

- + For symptomatic Grade 2 toxicity, the dose may be held until recovery to CTC Grade 0-1, then continue at the same dose or reduce by one level of temsirolimus and/or perifosine at the investigator's discretion. Grade 2 diarrhea does not require temporary discontinuation of treatment as this toxicity may improve despite continued treatment. For grade 2 diarrhea that is unacceptable to the patient for symptomatic reasons, hold perifosine temporarily held until resolution \leq grade 1 and subsequently re-started at the same dose. If symptomatic grade 2 diarrhea recurs after re-instituting treatment at the same daily dose and require temporary discontinuation, treatment of both agents should be held until resolution to \leq grade 1 and re-instituted at a reduced doses of both agents (see [Table 4, 5, and 6](#)).
- + In addition, areas of intratumoral micro-hemorrhage were noted on necropsy of mice harboring modeled GBMs following combined treatment of perifosine and temsirolimus. Significance of this in humans is unclear, and it may represent an early response to therapy. However, for patient safety, a non-contrast head CT or MRI with gradient echo imaging is required during the 2nd week of therapy to evaluate for such microbleeds. CTCAE grade 1 (asymptomatic, radiographic findings only) do not require treatment modification. CTCAE grade 2 (medical intervention indicated) may require corticosteroids as treatment for associated edema or other intervention at the discretion of the investigator, but treatment can continue at the discretion of the investigator.

Memorial Sloan Kettering Cancer Center
IRB Protocol

IRB#: 09-058 A(14)

- * Except nausea/vomiting (unless patients are on maximal antiemetic therapy) or hypercholesterolemia and hypertriglyceridemia and other Metabolism and Nutrition Disorders (such as hypophosphatemia and hypocalcemia) unless remaining grade 3 or unacceptable grade 2, despite maximal medical therapy.

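### Unacceptable grade 2 diarrhea that is not dose-limiting falls under two different dose rules, with nothing to say which governs

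*Combined protocol and SAP*

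**What the plan says.** Section 6.1.3 has a rule specific to diarrhea. "For grade 2 diarrhea that is unacceptable to the patient for symptomatic reasons", perifosine is held until grade 1 or better "and subsequently re-started at the same dose". Only if the diarrhea comes back after that restart and again needs a hold does the section escalate: "treatment of both agents should be held until resolution", and both are then restarted at reduced doses.

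Table 6, in its row for diarrhea, nausea and vomiting, takes the same first step. The perifosine column reads "Hold perifosine first. Resume at same dose after improvement", with a reduction only if there is no improvement. The temsirolimus column reads "If no improvement after holding perifosine, hold temsirolimus and reduce dose".

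Section 6.1.3.1, under maintenance dosing, has two steps for grade 2 nausea, vomiting or diarrhea. Step (a) keeps dosing and treats symptoms. Step (b) reads "For persistent nausea, vomiting or diarrhea despite symptomatic treatment that remains unacceptable to the patient", and the action is to "hold both agents and then reduce dose of each by one dose level".

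For other symptomatic grade 2 toxicity, section 6.1.3 lets the investigator hold and then "continue at the same dose or reduce by one level of temsirolimus and/or perifosine".

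**The concern.** Consider a patient who has had loperamide, as section 5.3.6 directs at first onset, and whose grade 2 diarrhea is still unacceptable. Section 6.1.3 and Table 6 send that patient to a perifosine-only hold and a same-dose restart, with temsirolimus continuing. Section 6.1.3.1(b) sends the same patient to a hold and a one-level cut of both drugs. Both actions comply with the protocol.

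The difference normally lasts. Sections 6.1.1 and 6.1.4 bar re-escalation after a reduction for drug toxicity; the exception in 6.1.1 is for events later judged unrelated to either drug. A cut under 6.1.3.1(b) also counts toward the two-reduction limit in 6.1.4. That limit can be waived by the investigator, PI and CTEP monitor, and 6.1.1 sets no such limit within a cycle above the 5 mg temsirolimus floor.

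Section 13.1 commits the phase I analysis to evaluating doses given, modifications and delays. Patients with the same event could therefore be recorded with different modifications because of which paragraph was followed, not because of how they tolerated the drugs.

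**Working it through.** The plan gives no figure to reproduce here. The check sets the rules side by side and then works out the dose consequence.

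**The rules for non-DLT, unacceptable grade 2 diarrhea**

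| | 6.1.3 | Table 6 | 6.1.3.1(b) |
|---|---|---|---|
| Trigger | Unacceptable to the patient | Diarrhea row | Persistent and unacceptable despite symptomatic treatment |
| First hold | Perifosine only | Perifosine only | Both drugs |
| Restart | Same dose | Same dose after improvement | Each one level lower |
| Both drugs reduced | On recurrence needing a hold | On no improvement | At once |

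**Does other text settle it?**

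1. *Is (b) a later step, after a failed perifosine hold?* Step (b) follows (a), which maintains dosing. Its trigger is failed symptomatic treatment, so no hold comes before it.
2. *Do the notes on toxicity manageable with supportive therapy decide?* They appear in 6.1.3 and 6.1.4. They say reduction is not required unless the toxicity stays unacceptable despite maximal therapy. They do not say whether a perifosine-only hold comes first.
3. *Is it a DLT, governed by 6.1.1?* Under 5.2.1, unacceptable grade 2 toxicity is a DLT when it interrupts dosing for more than 7 days in the first 28 days despite maximal treatment. Such events are reduced under 6.1.1 either way and lie outside this point. Shorter holds and later onsets remain.
4. *Does Table 7 govern?* Its general non-hematologic row excludes nausea, vomiting and diarrhea. Section 6.1.4 leaves events outside the table to investigator discretion, but at the start of a cycle, which does not settle the rule within one.

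**Size at the first episode**

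Perifosine maintenance, one level down in Table 5: 100 to 50 mg/day, (100 − 50)/100 = 50% lower.

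Temsirolimus, one level down in Table 4, where D is the current weekly dose and D′ the next lower one. The last columns illustrate the 28 days from the start of a hold, with one infusion missed under 6.1.3.1(b) and none under the other rule (4D against 3D′):

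| D to D′ (mg/week) | Cut per dose | 4D | 3D′ | Gap |
|---|---|---|---|---|
| 170 to 115 | 32.4% | 680 | 345 | 49.3% |
| 115 to 75 | 34.8% | 460 | 225 | 51.1% |
| 75 to 50 | 33.3% | 300 | 150 | 50.0% |
| 50 to 25 | 50.0% | 200 | 75 | 62.5% |
| 25 to 15 | 40.0% | 100 | 45 | 55.0% |
| 15 to 10 | 33.3% | 60 | 30 | 50.0% |

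The plan gives no hold length; 7 days is an assumption. On that assumption perifosine over the 28 days is 21 × 100 = 2,100 mg against 21 × 50 = 1,050 mg (50% lower). If no infusion falls in the hold, the temsirolimus gap at 75 mg is 4 × 75 = 300 against 4 × 50 = 200 mg (33.3% lower).

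**Nausea and vomiting**

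This is a looser case. The general sentence in 6.1.3 gives the investigator discretion, Table 6 resumes at the same dose, and 6.1.3.1(b) reduces both drugs. Section 5.1.1.2 calls for dose reduction if nausea recurs despite medical intervention, which partly supports 6.1.3.1(b).

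**The case against.** The best counter-reading is a ladder: treat symptoms under 6.1.3.1(a), hold perifosine under 6.1.3 if the diarrhea is unacceptable, then reduce both drugs under 6.1.3.1(b) if it is refractory. The triggers do differ in wording, and this may be what the authors meant. But the ladder needs a perifosine-hold step that (b) does not contain, so the reader has to supply it.

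Section 6.1.3 also points to Table 6 for dose adjustments, and Table 6 cites 6.1.3 for diarrhea but 6.1.3.1 for gout. That favors the stepwise rule. It is not conclusive, because 6.1.3.1 sits inside 6.1.3.

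The DLT wording could narrow the group. Section 6.1.4 repeats the diarrhea condition for DLT without the 7-day or 28-day clause, so refractory grade 2 diarrhea in later cycles might be read as a DLT and reduced under 6.1.1. Both that line and the footnote in 5.2.1 say diarrhea counts only if the condition is met. This makes the condition necessary, not sufficient, and leaves shorter holds and later events in dispute.

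Investigator discretion for symptomatic grade 2 toxicity shows the protocol tolerates either dose in general. It is followed by an instruction specific to diarrhea, so it does not remove the conflict.

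The points about scale stand. Section 7.1 lists diarrhea as likely (>20%) for both agents, but without a grade. The center's perifosine monotherapy trial lists one grade 1 diarrhea among significant related events in 25 patients (section 2.4). The 28-day gaps are individual illustrations, not expected effects. Both rules stop perifosine, so no safety failure is shown. A single institution and the PI contact in 6.1.5 limit the risk in practice.

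**Conclusion.** The concern holds: these are two stated rules with different outcomes for the same event, not missing detail. At the first episode they differ by 50% in perifosine maintenance (from 100 mg/day) and by 32% to 50% in the temsirolimus dose across planned levels 1 to 7. Under the assumed 7-day hold with one infusion missed, the 28-day temsirolimus gap is 49% to 63%.

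The effect is confined to patients with non-DLT diarrhea who would have tolerated a same-dose restart, because all three texts end in reduction of both drugs once the diarrhea recurs or does not improve. How many patients that is cannot be derived from the documents. No alpha, power, sample-size or DLT definition changes. It is worth correcting because the dose difference is normally permanent and the correction costs almost nothing.

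**What to change.** Reword 6.1.3.1(b) for diarrhea. After symptomatic treatment fails, hold perifosine first and resume it at the same dose on improvement; hold both agents and reduce each by one level only if there is no improvement or the diarrhea recurs. If immediate reduction of both drugs is what is wanted, change 6.1.3 and Table 6 to say so.

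For nausea and vomiting, state one rule across 6.1.3.1(b), Table 6 and 5.1.1.2. Keep the 5.1.1.2 requirement to reduce when nausea recurs despite medical intervention, and say whether the investigator discretion in 6.1.3 still applies.

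The cost is a wording amendment to these sections, with no change to design, sample size or analysis.

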6 DOSING DELAYS/DOSE MODIFICATIONS

6.1 Dose Modifications

Patients with stable or responding disease may be retreated at the same dose or at a reduced dose level, depending upon the adverse events observed in the current cycle and any adverse events present on the first day of the next cycle. If multiple toxicities are seen, the dose administered in a subsequent cycle should be based on the most

Amended:

Reviewed by OCR, JR 3/24/14

severe toxicity experienced in the current cycle. Dose modifications or delays should be made based upon whether toxicities occur within a 4-week treatment cycle or at the expected start of the next treatment cycle.

Patients who experience dose-limiting toxicity should have laboratory testing at least weekly until the toxicity has resolved.

6.1.1 Within Treatment Cycle:

If a patient experiences DLT (as defined in [Section 5.2](#)) during the current treatment cycle, the treatment will be immediately suspended for a minimum of 1 week. If the toxicity resolves to less than or equal to grade 1 (or to within 1 grade of starting values for pre-existing laboratory abnormalities) within 2 weeks of the last dose of both temsirolimus and perifosine (grade 2 for diarrhea and hyperlipidemia), the patient will be retreated at one or two dose levels lower (see [Section 6.1.2 - 6.1.5](#)). Patients experiencing DLT at the initial starting dose of temsirolimus of 15 mg i.v. weekly will have the dose reduced according to [Table 4](#). No dose reduction below 5 mg i.v. weekly is allowed. Otherwise, there is no limit on the number of dose level reductions. If temsirolimus-related toxicity persists at dose level -2 (5 mg i.v. weekly), the patient should be taken off study.

Doses that are reduced for temsirolimus or perifosine related toxicity will not be re-escalated, even if there is minimal or no toxicity with the reduced dose. Patients whose dose has been reduced for adverse events that are subsequently not felt to be related to temsirolimus or perifosine may have the dose re-escalated after completion of one cycle with toxicities less than or equal to grade 1. If any patient has further toxicities that would require additional reductions, or if treatment is held for more than 2 consecutive weeks because of ongoing toxicity, the investigator and the CTEP medical monitor will assess if the patient should remain in the study (if the patient has benefited from treatment).

Table 4: Temsirolimus Dose Modifications Table:

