6.1.2 Hematologic Toxicity

No dose adjustment or reduction of perifosine will be made for hematologic toxicity.

Dose Modifications of CCI-779 (Temirolimus) Based on Weekly ANC and Platelet Counts:

ANC (/mL)	Platelets (/mL)	% of Planned temsirolimus
≥ 1000	and ≥ 75,000	100%
750-999	or 50,000 to < 75,000	hold*
< 750	or < 50,000	hold**

* Upon recovery to ANC \geq 1,000/mL and platelets to \geq 100,000/mL, one lower dose level of temsirolimus will be administered (See [Table 4](#)). Patients already at the lowest dose level (5 mg i.v. weekly) will be removed from study.

** Upon recovery to ANC \geq 1,000/mL and platelets to \geq 100,000/mL, two lower dose levels will be administered. The exception will be patients at dose level -1 (10 mg i.v. weekly) who will be dose-reduced by only one level to 5 mg IV weekly (See [Table 4](#)). Patients already at the lowest dose level (5 mg i.v. weekly) will be removed from study.

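### After an ANC of 500-749, Section 6.1.2 cuts temsirolimus two levels and Table 7 cuts it one; a cycle Day 1 count falls under both rules and no precedence is stated

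*Combined protocol and SAP*

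**What the plan says.** - **Section 6.1** asks that dose changes be made "based upon whether toxicities occur within a 4-week treatment cycle or at the expected start of the next treatment cycle".
- **Section 6.1.2** works on weekly ANC and platelet counts. ANC 750-999, or platelets 50,000 to <75,000: hold, then one level down. ANC <750, or platelets <50,000: hold, and on recovery "two lower dose levels will be administered". A patient at 10 mg drops only to 5 mg, and a patient already at 5 mg leaves the study in either band. Recovery means ANC >=1,000 and platelets >=100,000.
- **Table 6**, hematologic row, temsirolimus column: "Hold drug and reduce dose per Section 6.1.2 and dose levels in table 4".
- **Section 6.1.4** (start of the next cycle) requires ANC >=1,000 and platelets >=100,000 on Day 1, and adds: "Dose adjustments for hematological toxicity are based on the blood counts obtained in preparation for the day of treatment". In its Table 7 the grade 3 row reads "Neutrophils ANC 500-1000 Platelets 50,000-75,000" and retreats one level down. The grade 4 row (ANC <500, platelets <25,000) retreats two levels down. Both rows delay the drug until grade 1 or better and stop all study treatment if recovery takes more than 14 days.
- For events outside Table 7: "If an adverse event is not covered in the table, doses may be reduced or held at the discretion of the investigator".
- On persistence of a cut: "Patients requiring dose reductions should not have the dose re-escalated with subsequent treatments". Section 6.1.1 says the same of reductions for drug-related toxicity.

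**The concern.** A patient whose ANC is 600 fits a row in Section 6.1.2 and a row in Table 7, and the two rows name different restart doses. This is two explicit instructions that disagree, not missing detail. Two patients with the same count could be restarted at different doses depending on which page was consulted. Because reductions for drug-related toxicity are not reversed, the difference would last for the rest of treatment. At stake are consistent dosing after neutropenia and a clean description of the dose delivered.

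**Working it through.** The plan states no figure to reproduce here. The check compares two rule sets and converts the result to mg.

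**Inputs.** Count bands from Sections 6.1.2 and 6.1.4 (Table 7); dose levels from Table 4: 5, 10, 15, 25, 50, 75, 115 and 170 mg/week. I read the two counts in a Table 7 row as alternatives and the upper ends of its ranges as exclusive.

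**Step 1: levels of reduction by band.**

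| Count | Section 6.1.2 | Table 7 |
|---|---|---|
| ANC 750-999 | 1 | 1 |
| **ANC 500-749** | **2** | **1** |
| ANC <500 | 2 | 2 |
| Platelets 50,000 to <75,000 | 1 | 1 |
| Platelets 25,000 to <50,000 | 2 | no row |
| Platelets <25,000 | 2 | 2 |

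The only conflicting doses are at ANC 500-749. The platelet line is an omission from one table.

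**Step 2: do both rules reach the same count?** Section 6.1.2 has no within-cycle limit, and Table 6 directs hematologic toxicity there whenever it occurs. Temsirolimus is given weekly, including Day 1 of each cycle, so a Day 1 count is within Section 6.1.2 and also within 6.1.4. In the Section 10 calendar, blood counts after week 4 fall in weeks 5, 7, 9 and 11. With 28-day cycles, weeks 5 and 9 open cycles 2 and 3, so 2 of those 4 scheduled counts are Day 1 counts. That is a share of scheduled counts, not of patients or episodes.

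**Step 3: restart dose after one episode at ANC 500-749.** Difference = 100 x (1 - Section 6.1.2 dose / Table 7 dose).

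| Current dose (mg/week) | Table 7 | Section 6.1.2 | Section 6.1.2 lower by |
|---|---|---|---|
| 170 | 115 | 75 | 34.8% |
| 115 | 75 | 50 | 33.3% |
| 75 | 50 | 25 | 50.0% |
| 50 | 25 | 15 | 40.0% |
| 25 | 15 | 10 | 33.3% |
| 15 | 10 | 5 | 50.0% |
| 10 | 5 | 5 | 0% |

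**Step 4: two episodes, both in this band.** From 75 mg: Table 7 gives 75 to 50 to 25; Section 6.1.2 gives 75 to 25 to 10. From the 15 mg phase I starting dose: Table 7 gives 15 to 10 to 5; Section 6.1.2 gives 15 to 5 and then removal, subject to the case-by-case review in Section 6.1.1. Longer sequences are not shown, because 6.1.4 withdraws a patient who would need a third reduction unless the investigator, PI and CTEP monitor agree otherwise.

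**Step 5: recovery before restarting.** Section 6.1.2 sets absolute counts (ANC >=1,000 and platelets >=100,000), while Table 7 sets a grade (1 or better). The protocol gives no counts for grade 1, so the documents alone do not show which is stricter or by how much. The length of a hold, and whether the 14-day limit is reached, could depend on which condition is used.

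**The case against.** The best defence is the timing split in Section 6.1: use 6.1.2 within a cycle and Table 7 at the start of the next. Much of this stands. Table 7 sits under the start-of-cycle heading, and the reference there to counts for the treatment day reads most naturally as Day 1, not as every weekly infusion. A reader might infer that the two rules clash throughout a cycle; the text does not support that. A reader might also cite Section 6.1.1, which says "the patient will be retreated at one or two dose levels lower" and points to Sections 6.1.2-6.1.5 together. That sentence applies only to a DLT. Under Section 5.2.1 neutropenia is a DLT by grade only at grade 4, and Table 7 labels ANC 500-1000 as grade 3, so it does not help here.

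What survives is the overlap on Day 1. Neither Section 6.1.2 nor Table 6 excludes Day 1 counts, and no sentence ranks the rules. Even under a strict split, the same ANC would earn a smaller cut at cycle start than mid-cycle, with no reason given.

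It is also tempting to call the platelet gap a second conflict, or to say that patients with platelets of 25,000 to <50,000 are left to discretion. Section 6.1.2 covers that band with a two-level cut, so if it applies throughout there is no gap in instruction.

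Practical mitigations are fair: Section 12.1 describes a single-institution study, Section 6.1.5 sends dose questions to the PI, and both rules hold the drug and lower the dose. The contact line helps less than it seems, since someone who finds a definite dose in either place has no cause to ask.

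**Conclusion.** The inconsistency is real but narrow. It concerns ANC 500-749 on a cycle Day 1 count in patients at 15 mg/week or more. There the Section 6.1.2 restart dose is 33-50% below Table 7's, and the difference persists unless the toxicity is later judged unrelated to the study drugs. The recovery condition differs as well. Table 7's missing platelet row is secondary.

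Frequency is unknown. The temsirolimus list in Section 7.1.1 places decreased neutrophil count in its <=20% column but gives nothing for this band, so no expected number of affected patients can be stated. The phase II dose is not fixed in the document, which is why the whole dose range is shown.

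A reader might infer a threat to the MTD or to the phase II error rates. The documents do not support that. The MTD rests on DLTs in the first 28 days, and the restart dose is not part of the DLT definition. One DLT criterion does turn on recovery within two weeks, but nothing in the documents shows that the two recovery wordings would classify a patient differently. The sample size and power calculations do not use these rules. This should be fixed as a dosing instruction.

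**What to change.** State in Section 6.1.4 that Section 6.1.2, as Table 6 already directs, governs hematologic holds, recovery thresholds and dose reductions at any time in a cycle. Align Table 7's Blood/Bone Marrow rows with it:

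- ANC 750-999 or platelets 50,000 to <75,000: hold until ANC >=1,000 and platelets >=100,000, then one level down.
- ANC <750 or platelets <50,000: hold to the same thresholds, then two levels down (10 mg goes to 5 mg).
- In either band, a patient already at 5 mg goes off study.

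Keep the Day 1 start criteria, the 14-day discontinuation rule and the third-reduction rule. Make clear that the Day 1 criteria take priority over Section 6.1.2's full-dose row, so that Day 1 platelets of 75,000 to <100,000 still delay the cycle.

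The change is one sentence and two table rows, with no added patients, visits or tests. Its clinical cost is one further level of reduction for patients with ANC 500-749 who would have been dosed from Table 7. If the sponsor prefers the milder cut, the conflict could be closed the other way, but Section 6.1.2 and Table 6 would then need changing and Table 7 would need a platelet row.
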